### Multiple Imputation procedures for missing PASI scores:

Intermittent missing values of PASI scores will be imputed separately for each treatment group using the Markov Chain Monte Carlo (MCMC) method, generating 50 copies of the imputed dataset with monotonic missing pattern. For each of the 50 datasets, missing values at scheduled visits (Weeks 4, 8, 12, 16, 20 and 24) will be imputed using a linear regression model. The imputations will include the following variables: baseline BMI, baseline PASI score, and PASI scores at the previous scheduled visits. SAS Proc MI will be used. Imputed PASI-75 response (Yes/No) will be derived for each imputed dataset.

Example SAS code is as follows:

```
PROC MI DATA = PASI1 OUT = PASI2 SEED = 132138 NIMPUTE = 50 NOPRINT;  
BY TRT01PN;
```

```
MCMC IMPUTE = MONOTONE;  
VAR BASEBMI BASEPASI _3 _4 _5 _6 _7 _8;  
RUN;  
  
PROC MI DATA = PASI2 OUT= PASI3 SEED = 132138 NIMPUTE = 1 NOPRINT;  
BY TRT01PN _IMPUTATION_;  
MONOTONE REGRESSION;  
VAR BASEBMI BASEPASI _3 _4 _5 _6 _7 _8;  
RUN;
```

Multiple Imputation procedures for missing IGA scores:

The imputation of post-baseline IGA scores will be performed following a similar approach as described for PASI scores. Intermittent missing IGA scores will be imputed separately for each treatment group using the Markov Chain Monte Carlo (MCMC) method where 50 copies of the dataset with monotonic missing pattern will be generated. For each of the 50 datasets, missing values at scheduled visits (Weeks 4, 8, 12, 16, 20 and 24) will be imputed using a logistic regression model including baseline BMI, baseline IGA score, and IGA scores at the previous scheduled visits. SAS Proc MI using the logistic regression method for monotone data will be used for the imputation. IGA Treatment Success status (Yes/No) will then be derived for each imputed dataset.

Example SAS code is as follows:

```
PROC MI DATA = IGA1 OUT = IGA2 SEED = 132138 NIMPUTE = 50 NOPRINT;  
BY TRT01PN;  
MCMC IMPUTE = MONOTONE;  
VAR BASEBMI _3 _4 _5 _6 _7 _8;  
RUN;  
  
PROC MI DATA = IGA2 OUT= IGA3 SEED = 132138 NIMPUTE = 1 NOPRINT;  
BY TRT01PN _IMPUTATION_;  
MONOTONE LOGISTIC;  
VAR BASEBMI _3 _4 _5 _6 _7 _8;  
RUN;
```

The imputation of missing post-baseline BSA, PSSI final score, NAPSI, and NRS scores will be performed using a similar method as described for PASI. The imputation of missing post-baseline PP PGA scores will be performed using a similar method as described for IGA. A pre-specified seed number of 132138 will be used in all imputation procedures. No imputation will be done to the health-related quality of life endpoints or safety endpoints.

- **Observed cases (OC)**: No imputation will be performed, only observed values will be analyzed.
- **m-NRI (response endpoint only)**: Subjects who used rescue medications or discontinued due to unsatisfactory therapeutic effect are considered as treatment failures (i.e., non-responder) for all time points after the initiation of rescue medications or subject discontinuation. For example, if a subject discontinued due to lack of efficacy, all visits

after the last planned visits will be imputed to non-responders. If a subject used rescue medication during the study, all visits after the start of the rescue medication will be imputed to non-responders regardless if the subject had an assessment or not. Other subjects with missing data will be kept as missing (i.e., no imputation). Discontinuation due to unsatisfactory therapeutic effect will be identified by discontinuation reason = "Other" with a comment "lack of efficacy" on the eCRF.

- **LOCF:** The last observed value will be carried forward for any subsequent missing values. Baseline values will not be carried forward.

A summary of the imputation methods for all efficacy endpoints is shown below:

Endpoint	Analysis Population	Imputation Methods
PASI-75 at Week 24	FAS	MI, m-NRI, LOCF, OC
	PP	m-NRI
IGA score of clear or almost clear at Week 24	FAS	MI, m-NRI, LOCF, OC
	PP	m-NRI
Change from Baseline and percent change from Baseline in PASI Total Score by Visit	FAS	MI, LOCF, OC
	PP	OC
PASI-50 and PASI-75 by Visit	FAS	MI, m-NRI, LOCF, OC
	PP	m-NRI
IGA score of clear or almost clear by Visit	FAS	MI, m-NRI, LOCF, OC
	PP	m-NRI
Change from Baseline and percent change from Baseline in BSA by Visit	FAS	MI, LOCF, OC
	PP	OC
Change from Baseline in NPSI by Visit	FAS	MI, LOCF, OC
	PP	OC
Change from Baseline in PSSI by Visit	FAS	MI, LOCF, OC
	PP	OC
Change from Baseline in PP PGA by Visit	FAS	MI, LOCF, OC
	PP	OC
Change from Baseline in NRS by Visit	FAS	MI, LOCF, OC
	PP	OC
Time to PASI-75	FAS	OC
Time to achieving an IGA score of clear or almost clear	FAS	OC
QIDS-SR 16	FAS	OC
DLQI	FAS	OC
SF-12	FAS	OC
WPAI:PSO	FAS	OC

HEOR	FAS	OC
------	-----	----

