## 7. SAMPLE SIZE DETERMINATION

It was determined that a sample size of 100 subjects per treatment group would detect a significant difference in proportion of PASI-75 and IGA responders from Baseline to Week 24 between each dose group of PPC-06 and placebo group, assuming a 15% response rate for the placebo group and 45% for PPC-06 at Week 24. To provide sufficient evidence of treatment effect, both PASI and IGA based response rate must reject at the same significance level. The hypothesis testing for the three dose groups will be conducted sequentially from high to low dose (600 mg BID, 400 mg BID and 400 mg QD); therefore, the 2-sided Type I error rate from a chi-squared test remains at the 0.05 level. Assuming 50% dropout rate, about 100 subjects per treatment arm will be randomized to get approximately 50 completers in each treatment arm. The total sample size of 400 subjects will yield at least 84% power for hypothesis testing of the co-primary endpoints of a difference in PASI-75 and IGA responders from Baseline to Week 24 between PPC-06 doses and placebo.

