## 11.5 Pooled Analysis Centers

There will be approximately 75 trial sites in the United States. Pooling of trial sites, based on insufficient number of subjects, will be performed when any site does not have a minimum number (e.g., 5 subjects per site per arm) of subjects in the FAS population. Sites with insufficient number

of subjects will be combined in order of geographical proximity. The exact composition of these “analysis sites” will be determined and documented prior to breaking the trial blind.

Descriptive summaries of the co-primary efficacy endpoints will be provided for each analysis site. Any notable site heterogeneity will be further investigated. Exploratory analyses of the co-primary endpoints may be performed excluding analysis sites whose results differ appreciably from other analysis sites.

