### **12.8.4 Subgroup Analyses**

The co-primary efficacy endpoints will be analyzed for the following subgroups:

- Baseline hsCRP (< 5 mg/L, >=5 mg/L)
- Baseline BMI (<30, >=30)
- Occurrence of diarrhea (Subjects reported diarrhea as adverse event by Week 24, subject did not report diarrhea by Week 24)

The same method as described in [Section 12.8.1](#) will be used for the subgroup analyses, except that no formal hypothesis testing will be performed.

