14.2.1.3.2	Analysis of Co-Primary Efficacy Outcome, Subgroup Analysis, PASI-75 Response Rate at Week 24 by Baseline BMI, Full Analysis Set, Multiple Imputation
14.2.1.3.3	Analysis of Co-Primary Efficacy Outcome, Subgroup Analysis, PASI-75 Response Rate at Week 24 by Occurrence of Diarrhea, Full Analysis Set, Multiple Imputation
14.2.1.4.1	Analysis of Co-Primary Efficacy Outcome, Subgroup Analysis, IGA Treatment Success Rate at Week 24 by Baseline hsCRP (mg/L), Full Analysis Set, Multiple Imputation
14.2.1.4.2	Analysis of Co-Primary Efficacy Outcome, Subgroup Analysis, IGA Treatment Success Rate at Week 24 by Baseline BMI, Full Analysis Set, Multiple Imputation
14.2.1.4.3	Analysis of Co-Primary Efficacy Outcome, Subgroup Analysis, IGA Treatment Success at Week 24 by Occurrence of Diarrhea, Full Analysis Set, Multiple Imputation
14.2.1.5.1	Analysis of Co-Primary Efficacy Outcome, PASI-75 Response Rate at Week 24 by Visit and Analysis Sites, Full Analysis Set, Multiple Imputation
14.2.1.5.2	Analysis of Co-Primary Efficacy Outcome, IGA Treatment Success at Week 24 by Visit and Analysis Sites, Full Analysis Set, Multiple Imputation
14.2.2	Summary of Secondary Efficacy Tables
14.2.2.1.1.1	Analysis of Secondary Efficacy Outcome - Change from Baseline in Total PASI Score by Visit, Double-Blind Treatment Period, Full Analysis Set, Multiple Imputation
14.2.2.1.1.2	Analysis of Secondary Efficacy Outcome - Percent Change from Baseline in Total PASI Score by Visit, Double-Blind Treatment Period, Full Analysis Set, Multiple Imputation

14.2.2.1.2.1	Analysis of Secondary Efficacy Outcome - Change from Baseline in Total PASI Score by Visit, Double-Blind Treatment Period, Full Analysis Set, LOCF
14.2.2.1.2.2	Analysis of Secondary Efficacy Outcome - Percent Change from Baseline in Total PASI Score by Visit, Double-Blind Treatment Period, Full Analysis Set, LOCF
14.2.2.1.3.1	Analysis of Secondary Efficacy Outcome - Change from Baseline in Total PASI Score by Visit, Double-Blind Treatment Period, Full Analysis Set, OC
14.2.2.1.3.2	Analysis of Secondary Efficacy Outcome - Percent Change from Baseline in Total PASI Score by Visit, Double-Blind Treatment Period, Full Analysis Set, OC
14.2.2.1.4.1	Analysis of Secondary Efficacy Outcome - Change from Baseline in Total PASI Score by Visit, Double-Blind Treatment Period, PP Population, OC

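### Baseline hsCRP defines a planned subgroup but is left out of the imputation model, so hsCRP differences in the imputed tables are pulled toward the arm average

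*SAP*

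**What the plan says.** SAP Section 9 imputes PASI separately by treatment group: an MCMC step for intermittent gaps, then sequential regression. On the predictors it says: "The imputations will include the following variables: baseline BMI, baseline PASI score, and PASI scores at the previous scheduled visits". The IGA imputation is described in the same way with a logistic step. The example code for both endpoints lists BMI and the visit scores (plus baseline PASI for PASI), and no hsCRP.

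SAP Section 12.8.4 breaks the co-primary endpoints down by three subgroups, the first being "Baseline hsCRP (< 5 mg/L, >=5 mg/L". It applies the primary method without formal hypothesis testing. In Section 16 the hsCRP tables (14.2.1.3.1 for PASI-75, 14.2.1.4.1 for IGA) are listed only on the Full Analysis Set with multiple imputation. Their shell shows response rates averaged over 50 imputed datasets, with PPC-06 against placebo odds ratios, confidence intervals and p-values within each hsCRP stratum.

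The planning assumption on missing data is in SAP Section 7: "Assuming 50% dropout rate, about 100 subjects per treatment arm will be randomized to get approximately 50 completers in each treatment arm".

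**The concern.** If a variable defines a comparison but is absent from the imputation model, missing values are drawn as though it had no effect beyond what the included predictors carry. Here a subject with high hsCRP who leaves early is completed from the pattern of the whole arm, given BMI and the scores seen so far. With about half of Week 24 values planned to be missing, a large part of each hsCRP cell could be filled this way.

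BMI, the other baseline subgroup variable, is in the model, so the gap is specific to hsCRP. Because no hsCRP table is listed under another missing-data method, nothing in the planned output would reveal the attenuation. At stake is whether the trial can show that response, or drug effect, differs by baseline inflammation. A reader of these tables could take an artefact of imputation for the absence of a difference.

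**Working it through.** **1. The plan's own figure.** SAP Section 7 gives these inputs: "assuming a 15% response rate for the placebo group and 45% for PPC-06 at Week 24", two-sided 0.05, 100 randomized and 50 completers per arm. With pooled rate 0.30:

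- SE under the null = sqrt(2 × 0.30 × 0.70 / 50) = 0.0917
- SE under the alternative = sqrt((0.15 × 0.85 + 0.45 × 0.55) / 50) = 0.0866
- z = (0.30 − 1.96 × 0.0917) / 0.0866 = 1.39, so power per endpoint = 0.918
- both endpoints, taken as independent: 0.918² = 0.842

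This reproduces the stated 84% and confirms that 50% missing at Week 24 is the plan's own working basis.

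**2. Ceiling.** Let D be the true difference in response rate between hsCRP groups within an arm, m the share missing at Week 24 (taken as equal in both groups), and r the fraction of D that BMI and earlier scores pass on to the imputed values. Then

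D shown = (1 − m)D + m·r·D, so loss = m(1 − r).

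With m = 0.50, r = 0 gives 50%, which is the ceiling. A loss of 40% corresponds to r = 0.2, and 20% to r = 0.6.

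**3. Simulation.** The documents do not give r, so it was explored by large-sample simulation (200,000 subjects in one arm). Assumptions: percent change in PASI at six visits; Week 24 means −55 and −85 in the two groups with SD 35, so true PASI-75 rates are Φ(−20/35) = 28.4% and Φ(10/35) = 61.2%; 50% monotone dropout at random with at least one post-baseline visit; hsCRP unrelated to BMI and baseline PASI; sequential regression imputation without the group variable. Loss = 1 − (difference shown / true difference), in percent, by AR(1) correlation:

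| Dropout timing | Course of the group difference | 0.70 | 0.85 | 0.95 |
|---|---|---|---|---|
| Mostly early | ramp to Week 24 | 43.9 | 37.4 | 31.8 |
| Mostly early | plateau by Week 12 | 36.3 | 26.7 | 15.9 |
| Uniform | ramp | 34.7 | 28.0 | 22.4 |
| Uniform | plateau | 25.9 | 15.2 | 5.0 |
| Mostly late | ramp | 28.5 | 21.5 | 15.8 |
| Mostly late | plateau | 20.2 | 9.7 | 1.7 |

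A wider grid, run separately, added exchangeable correlation and late-emerging differences. Median loss (range) was 41% (22-49%) if all dropouts leave after Week 4, 36% (16-47%) mostly early, 28% (6-39%) uniform and 22% (2-32%) mostly late. One case from it (uniform, 0.85, ramp): 61.0% against 28.6%, a true gap of 32.5 points, is shown as 23.1; 1 − 23.1/32.5 = 29%. At 30% dropout, losses were 1-30% (medians 13-25%). At 20% dropout, all were under 20% (medians 9-16%).

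**4. With hsCRP group in the model.** Loss was −1.3% to +0.9% across the table's scenarios, which is simulation noise. In a separate run at trial size (100 per arm, 50% dropout), a true gap of 40.8 points was shown as 31.3 (−23%) as planned and 38.5 (−6%) with hsCRP added. A gap of 27.6 was shown as 21.2 (−23%) and 26.6 (−4%).

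**5. Drug against placebo within a stratum.** A further simulation (correlation 0.8, uniform 50% dropout, ramp, no BMI or baseline covariates) gave drug-placebo differences in response rate, in points:

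| hsCRP effect | Stratum 1, true → shown | Stratum 2, true → shown | Difference between strata |
|---|---|---|---|
| Prognostic only | 34.6 → 32.0 | 20.2 → 22.5 | 14.4 → 9.5 |
| Modest effect modification | 37.7 → 34.3 | 21.4 → 23.8 | 16.3 → 10.5 |
| Very large effect modification | 49.5 → 42.5 | 11.3 → 16.6 | 38.2 → 25.9 |

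The SD of the imputed estimates was 8-10 points.

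**The case against.** Much of the case for leaving the plan alone is sound. The subgroup analyses carry no formal testing. The shell's main output is drug against placebo within each stratum, and there a purely prognostic hsCRP effect moves each contrast by only 2 to 3 points, well inside sampling noise. The simulated gaps between hsCRP groups (28 to 41 points) are close to or larger than the whole planned drug effect of 45 − 15 = 30 points, and nothing in the documents supports gaps of that size. At 20-40% loss, a 10-point gap would lose 2 to 4 points. The 50% figure refers to randomized subjects: the Full Analysis Set drops those with no post-dose efficacy assessment, and under SAP Section 11.4 an early-termination assessment from Day 155, within 15 days of last dose, counts as Week 24. Both may lower the missing share. All this limits the size. None of it supplies a reason to omit the variable.

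Three stronger readings are tempting, and the documents do not support them.

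- That a quarter to a half of any hsCRP difference is lost. This needs dropout timing, correlation and time course that the plan does not give, and one half is the ceiling.
- That the primary result is biased. Imputation is by arm, and none of the simulations shows the same shrinkage in the overall drug-placebo contrast.
- That the by-site tables should be switched to observed cases. Tables 14.2.1.5.1 and 14.2.1.5.2 do share the shrinkage (2-45% with ten simulated centers), and SAP Section 11.5 says: "Any notable site heterogeneity will be further investigated". But that section sets no threshold and makes exclusion of sites optional and exploratory. With its example of 5 subjects per site per arm and 50% dropout, half of the cells would have two or fewer observed subjects (binomial probability 16/32) and 1/32, or 3%, would have none. In simulation, root mean squared error of site gaps was 28-34 points on observed cases against 20 under the planned imputation. That is a trade of bias for variance, not a correction.

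**Conclusion.** The concern holds for baseline hsCRP. The imputation model omits a variable that defines a planned subgroup table, and that table exists only in imputed form. Differences in response between hsCRP groups, and any hsCRP-by-treatment effect modification, are attenuated toward the arm average. At the planned 50% dropout the loss is at most about one half, roughly 20-40% in central scenarios, and as little as a few percent if dropout is lower or later or within-subject correlation is strong. In the simulated cases of effect modification, the difference between strata lost about a third (36% and 32%).

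These sizes assume data missing at random and hsCRP unrelated to BMI and baseline PASI; any such relation would reduce the loss. They were computed for PASI-75. The mechanism applies to IGA, but its size there was not computed. The affected outputs are descriptive, so this is an improvement to a secondary output and not a threat to the primary conclusion.

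**What to change.** Add baseline hsCRP to the VAR list of both PROC MI steps for PASI and for IGA, ahead of the visit scores, either on the log scale or as the indicator for 5 mg/L or more. Make the same addition in the text of SAP Section 9. Because imputation runs separately by arm, one term lets the hsCRP effect differ between arms. If the primary imputation is to stay as it is, make the change at least in the imputations that feed Tables 14.2.1.3.1 and 14.2.1.4.1, and say so in the footnotes.

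The cost is SAP wording and one extra parameter per imputation regression, with about 100 subjects randomized per arm. No new data are needed: Protocol Table 1-1 includes hsCRP in the laboratory assessments at Screening and Baseline, and the baseline rule in SAP Section 11.3 takes the last value before first dose. If separate imputations are used, the subgroup tables will not average exactly to the primary result.

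For the by-site tables, no change of method is required. At most, print the number observed at Week 24 per site and arm beside the imputed rates.

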5.4 Discontinuation of Treatment or Assessments

Subjects can be removed from the study for any of the following reasons:

- AE(s)
- Protocol violation
- Withdrawal by subject (subject voluntarily discontinued study participation)
- Lost to follow-up
- Pregnancy
- Study terminated by sponsor
- Investigator decision
- Non-compliance with study drug (<80% or >120%)
- Loss of ability to freely provide consent through imprisonment or involuntary incarceration for treatment of either a psychiatric or physical (eg, infectious disease) illness
- Unblinding of a subject for any reason

All subjects meeting the above withdrawal criteria are to be evaluated at the safety follow-up EOS visits unless they have withdrawn full consent. The reason for a subject's permanent withdrawal is to be recorded on the appropriate electronic case report form (eCRF). Subjects

who prematurely withdraw from the study for AEs are to be monitored for up to 30 days after the subject stopped study treatment or until the abnormal parameter resolves or stabilizes.

Pregnancies are to be reported to the sponsor or designee within 24 hours of learning of its occurrence, and the pregnancy is to be monitored to determine outcome. Investigators are to document their attempts to contact subjects who are lost to follow-up.

As a class, FAEs are known to have an effect on lymphocyte and eosinophil counts and can have hepatotoxic and nephrotoxic effects at excessive exposures. The following study drug discontinuation criteria are to be implemented to reduce the risk of toxicity for individual subjects and to investigate the time course of recovery of affected safety parameters.

If any of the following criteria are met, study treatment will be permanently discontinued and the subject will be scheduled for an ETV followed by the Safety Follow-up Visit.

- Lymphocytes $<500/\text{mm}^3$ at any visit
- Lymphocytes $<800/\text{mm}^3$ on 3 consecutive visits
- ALT or AST $>8\times\text{ULN}$ on repeat examination (if assumed increase is related to study drug)
- ALT or AST $>5\times\text{ULN}$ for more than 2 weeks on repeat examination (if assumed increase is related to study drug)
- ALT or AST $>3\times\text{ULN}$ and either total bilirubin $>2 \times$ the ULN or International Normalized Ratio (INR) >1.5 on repeat examination (if assumed increase is related to study drug) in presence of normal alk phosphate.

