MI for missing IGA scores : The imputation of post-baseline IGA scores will be performed following a similar approach as described for PASI scores. Intermittent missing IGA scores will be imputed separately for each treatment group using the Markov Chain Monte Carlo (MCMC) method where 50 copies of the dataset with monotonic missing pattern will be generated. For each of the 50 datasets, missing values at scheduled visits (Weeks 4, 8, 12, 16, 20 and 24) will be imputed using a logistic regression model including baseline BMI, baseline IGA score, and IGA scores at the previous scheduled visits. SAS Proc MI using the logistic regression method for monotone data will be used for the imputation. IGA Treatment Success status (Yes/No) will then be derived for each imputed dataset.

The imputation of missing post-baseline BSA, NAPSI, and NRS scores will be performed using a similar method as described for PASI. The imputation of missing post-baseline PSSI and PP PGA scores will be performed using a similar method as described for IGA. No imputation will be done to the health-related quality of life endpoints or safety endpoints and only observed values will be analyzed.

mNRI: Subjects who used rescue medications or discontinued due to unsatisfactory therapeutic effect are considered as treatment failures (i.e., non-responder) for all time points after the initiation of rescue medications or subject discontinuation. Other missing data are not to be imputed and are to be kept as missing.

LOCF: The last observed value will be carried forward for any subsequent missing values. Baseline values will not be carried forward.

All QoL endpoints will be analyzed using the OC approach. No other imputations will be made unless otherwise specified.

Note that Early Termination visit data will be analyzed at the closest visit where data are not obtained. Full details will be provided in the SAP.

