## 8. ANALYSIS POPULATIONS

The following analysis sets/populations will be used in this trial:

- Safety population: include all subjects who receive at least one dose of IP. The safety population is the population used for all safety analyses.
- Full analysis set (FAS) – All randomized subjects who receive at least one dose of investigational product and have at least one post dose efficacy assessment. The FAS population will be the primary population for the efficacy analyses
- Per Protocol (PP) population: include subjects in the FAS population who complete the study without any major protocol violations that are considered likely to affect the efficacy analysis outcomes of the study. Major protocol violations will include but not be restricted to the following:
  - Failure to meet the inclusion/exclusion criteria that are considered likely to affect the efficacy analysis outcomes of the study
  - Randomization error

- Usage of any prohibited concomitant medications or procedures
- Failure to have Week 24 assessment within the allowable window for either of the co-primary endpoints
- Failure to be compliant with treatment regimen

Additional criteria may be added to determine PP population. The composition of the PP population will be determined and documented in blind reviews of the database conducted prior to unblinding the study database. Subjects who used rescue medications or who discontinued due to unsatisfactory therapeutic effect will be included in the PP population. These subjects will be considered as treatment failures (i.e., non-responder for both PASI-75 and IGA) for all time points after the initiation of rescue medications or subject discontinuation.

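### SAP section 9 recognises lack-of-efficacy withdrawals only as 'Other' plus a set comment, so those recorded otherwise drop out of m-NRI and PP instead of counting as failures

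*SAP*

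**What the plan says.** Protocol section 8.7.3 sets the intent for m-NRI: "Subjects who used rescue medications or discontinued due to unsatisfactory therapeutic effect are considered as treatment failures" from that point on. It attaches no condition on how the discontinuation was coded. SAP section 9 repeats the rule and leaves all other missing data missing. SAP section 8 carries the same idea into the PP population: "Subjects who used rescue medications or who discontinued due to unsatisfactory therapeutic effect will be included in the PP population", where they count as non-responders on both co-primary endpoints.

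SAP section 9 then adds the working definition: "Discontinuation due to unsatisfactory therapeutic effect will be identified by discontinuation reason". The reason named is 'Other', with a comment of lack of efficacy. Table 14.1.1 has a 'Lack of efficacy' row, but the footnote to its 'Other' row shows that the split is made by the same comment. It is not shown as a separately collected reason.

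Protocol section 5.4 lists ten reasons for removal. They include "Withdrawal by subject (subject voluntarily discontinued study participation") and investigator decision, but neither lack of efficacy nor 'Other'. SAP section 13, which records changes from the protocol, does not mention the narrower definition.

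**The concern.** A site whose subject leaves because the psoriasis has not improved can record that under at least two of the reasons in Protocol section 5.4. No record made under either can meet the SAP definition, whatever the comment says. The subject is then treated like any other dropout, although the plan calls for a failure.

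Among the planned methods for the responder endpoints, m-NRI is the only one that sets these dropouts to non-response because they left for lack of effect. Multiple imputation (MI) imputes them, LOCF carries their last value forward, and observed-case analysis omits them. If the flag misses them, m-NRI moves towards the observed-case analysis, apart from rescue users. What is at stake is whether these outputs do what they state:

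- the m-NRI sensitivity analysis in the full analysis set;
- the supporting m-NRI analysis in PP;
- the by-visit m-NRI tables for PASI-50, PASI-75 and IGA;
- the m-NRI part of the blinded interim looks;
- the 'Lack of efficacy' row of Table 14.1.1.

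**Working it through.** **Step 1: trace one subject.** Take a subject who stops early because psoriasis persists, uses no rescue medication and has no Week 24 value.

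| How the withdrawal is recorded | m-NRI at Week 24 | PP |
|---|---|---|
| 'Other', comment lack of efficacy | non-responder | kept as a failure |
| 'Other', other wording (e.g. psoriasis worse) | missing if the rule is read literally | excluded if read literally |
| Subject withdrawal or investigator decision | missing | excluded: did not complete, no Week 24 assessment |

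MI imputes the Week 24 score in all three rows. LOCF carries forward the last post-baseline value in all three. The reason code enters neither.

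**Step 2: the plan's own figure.** SAP section 7 gives the inputs: "assuming a 15% response rate for the placebo group and 45% for PPC-06 at Week 24"; "Assuming 50% dropout rate, about 100 subjects per treatment arm will be randomized to get approximately 50 completers in each treatment arm"; two-sided 0.05; both endpoints required. For one endpoint with 50 per arm:

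- (0.30 − 1.96 × √(2 × 0.30 × 0.70/50)) / √((0.15 × 0.85 + 0.45 × 0.55)/50) = (0.30 − 0.1796)/0.0866 = 1.390, which gives power 0.918.
- For two endpoints taken as independent, 0.918² = 0.842.

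This matches the stated figure: "The total sample size of 400 subjects will yield at least 84% power for hypothesis testing of the co-primary endpoints". With 100 per arm the joint power would be 0.995, so the plan's figure rests on 50 completers per arm. The point under review does not change it.

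**Step 3: placebo rate under m-NRI (illustration).** With 50 completers, placebo responders are 0.15 × 50 = 7.5. If L dropouts leave for lack of efficacy and a share c is identified, the rate is 7.5/(50 + cL). The documents give no split of dropout by reason, so L is assumed.

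- L = 25: all identified 7.5/75 = 10%; half 7.5/62.5 = 12%; none 7.5/50 = 15%.
- L = 10, all identified: 7.5/60 = 12.5%.
- L = 40, all identified: 7.5/90 = 8.3%.

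**Step 4: the treatment contrast.** Active responders are 0.45 × 50 = 22.5. With Lp placebo and La active efficacy dropouts, all identified, the odds ratio is [22.5/(27.5 + La)] / [7.5/(42.5 + Lp)] = 3 × (42.5 + Lp)/(27.5 + La). With none identified it is 3 × 42.5/27.5 = 4.64, and the rates are 15.0% and 45.0%, a difference of 30.0 points.

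| Lp, La | Placebo, active (all identified) | Difference | Odds ratio | Odds ratio if none identified |
|---|---|---|---|---|
| 10, 5 | 12.5%, 40.9% | 28.4 points | 4.85 | 4.64 |
| 20, 10 | 10.7%, 37.5% | 26.8 points | 5.00 | 4.64 |
| 30, 10 | 9.4%, 37.5% | 28.1 points | 5.80 | 4.64 |
| 20, 20 | 10.7%, 32.1% | 21.4 points | 3.95 | 4.64 |

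On these figures, and with the same share missed in both arms, missing the dropouts lowers the odds ratio when Lp/La exceeds 42.5/27.5 = 1.55 and raises it otherwise. The risk difference rises in these four splits, but not in general. With 20 placebo and no active efficacy dropouts it would fall from 45.0 − 10.7 = 34.3 to 30.0 points.

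**The case against.** Much of the case on the other side stands.

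- **Scope.** MI explicitly includes those who left for unsatisfactory effect and does not set them to non-response. LOCF ignores the reason code and will usually carry forward a non-response for a subject who leaves unimproved. Rescue users are failures under a separate rule. For the interim looks, two of the three methods ignore the code and the reported rate is pooled across arms.
- **Unseen material.** Protocol section 5.4 is not the eCRF pick-list, and the SAP shows that the eCRF does hold 'Other' with a comment. How sites would code such a subject, and how many would be missed, is not in the documents.
- **Strictness of the rule.** The SAP does not say that the comment must match word for word, so data review might accept equivalent wording under 'Other'. That does not help a withdrawal recorded under a different reason, which fails the rule on any reading.
- **Timing.** The synopsis plans the study for November 2017 to January 2019. The SAP dates from 15 November 2018, with an amendment on 15 April 2019. A new eCRF reason would probably come too late.

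Three stronger readings are tempting. A reader might infer that the co-primary result is biased; it is not touched, because the reason code does not enter MI. A reader might expect efficacy dropout to be commonest on placebo and infer a bias towards PPC-06. Step 4 shows that a clear placebo excess moves the odds ratio, the reported measure, down. A reader might also conclude that the 'Lack of efficacy' row is too low. The documents show only that it omits any such withdrawal recorded elsewhere.

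None of this removes the fault. The SAP states a positive rule that is narrower than the intent in Protocol section 8.7.3 and SAP section 8.

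**Conclusion.** The point holds for the outputs that use the efficacy-withdrawal flag. Withdrawals for insufficient effect that are recorded under another reason, or in other wording if the rule is applied literally, would stay missing in m-NRI and be excluded from PP. The m-NRI response rate rises in any arm where that happens. In the illustration the placebo rate goes from 10% with full identification to 15% with none.

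The size rests on assumptions that the documents cannot confirm: 25 efficacy dropouts among 50, no rescue use and no Week 24 value among them, and response rates that apply to completers. With 50% planned dropout there is room for a material effect, but neither its size nor its direction on the odds ratio can be stated. This should be corrected before unblinding. It gives no reason to doubt the primary analysis.

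**What to change.** In SAP section 9, replace the definition with one that covers any discontinuation, under any recorded reason, whose reason or comment attributes it to insufficient effect or worsening psoriasis, as classified in the blinded review that SAP section 8 already plans before unblinding. Use this single flag in m-NRI (full analysis set, PP and by visit), in the PP inclusion rule, in Table 14.1.1, and in any interim look still to come. This restores the scope of Protocol section 8.7.3, so it is not a departure from the protocol.

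Add a coded lack-of-efficacy reason to the eCRF only if data collection is still open. It would not by itself recode earlier withdrawals.

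The cost is one more item in a review that is already scheduled. The downside is a small amount of judgement in reading comments, made blind to treatment. The review can find only what sites wrote down, and the documents do not show whether comments are collected for reasons other than 'Other'.
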